## **8.5. Treatment-Emergent Adverse Events**

A TEAE is defined as an AE that occurred during the clinical trial after the first dose of IP or was present prior to dosing and exacerbates after the first dose of IP.

## **8.6. Serious Adverse Events**

An SAE is any AE that results in any of the following outcomes:

- death;
- a life-threatening AE;
- Note: An AE is considered “life-threatening” if, in the view of either the investigator or Sponsor/designee, the subject is at immediate risk of death as a result of the AE.

■ "Life-threatening" does not include an AE that, had it occurred in a more severe form, might have caused death.

- inpatient hospitalization or prolongation of existing hospitalization;
  - Note: The term "inpatient hospitalization" refers to any inpatient admission (even if less than 24 hours). For chronic or long-term subjects, inpatient admission includes transfer within the hospital to an acute/intensive care inpatient unit. Inpatient hospitalization does not include emergency room visits; outpatient/same-day/ambulatory procedures; or admission to observation/short-stay units, rehabilitation facilities, hospice facilities, nursing homes, or clinical research/Phase 1 units.
  - Note: The term "prolongation of existing hospitalization" refers to any extension of an inpatient hospitalization beyond the stay anticipated or required for the reason for the initial admission, as determined by the investigator or treating physician.
- a persistent or significant incapacity or substantial disruption of the ability to conduct normal life functions;
  - Note: A serious adverse event (SAE) specifically related to visual threat would be interpreted as any potential impairment or damage to the subject's eyes (e.g., hemorrhage, retinal detachment, central corneal ulcer, or damage to the optic nerve).
- a congenital anomaly/birth defect; and,
- other serious (Important Medical Events) events that do not fit other outcomes, where the event may jeopardize the subject and may require medical or surgical intervention to prevent one of the outcomes listed in the SAE definition, based upon appropriate medical judgment.

#### **8.6.1.      Unexpected Adverse Event**

An unexpected adverse event is defined as an AE, the nature or severity of which is not consistent with the information in the Investigator's Brochure.

#### **8.6.2.      Reporting Serious Adverse Events**

The investigator is responsible for reporting all SAEs, regardless of causality, to the Sponsor designee within 24 hours of learning of the occurrence. SAEs should be captured in the eCRF. If the SAE paper form is used, it should be sent to [NorthAmerica\\[contact]](mailto:[contact]) or faxed ([name]). An SAE "hot-line" is available to site personnel: [name] (during Eastern US business hours, Monday –Friday, 8:30 AM until 5:00 PM). Local toll-free numbers will be provided on the SAE report form cover sheet.

The reporting timeframe starts when the subject signs the informed consent or assent form through 30 days after the last IP administration. At a minimum, a description of the event and the Investigator's judgment of causality must be provided at the time of the initial report. These preliminary reports will be followed by detailed descriptions that will include copies of hospital case reports, autopsy reports, and other documents when requested and applicable.

A follow-up SAE Report must be submitted within 24 hours of the investigator receiving the follow-up information (such as information regarding complications, progression or resolution).

An SAE that is considered completely unrelated to a previously reported event should be reported separately as a new SAE.

The procedures for reporting SAEs are as follows:

- Complete the SAE eCRF or “Serious Adverse Event Report Form”. The investigator may contact Pharmacovigilance via the telephone hotline for assistance with SAE reporting.
- If the “Serious Adverse Event Report Form” is utilized, fax or email the SAE Form to the attention of Pharmacovigilance within 24 hours of the investigator’s knowledge of the event.

The original copy of the SAE Report Form and the fax confirmation sheet (or email) must be kept with the source documentation at the clinical trial site.

Follow-up information should be communicated the same way, using a new SAE Report Form stating that it is a follow-up to the previously reported SAE and giving the date of the original report. The follow-up information should describe whether the event has resolved or continues, if and how it was treated, and whether the subject continued or withdrew from clinical trial participation.

The investigator and qualified site staff should institute any supplemental investigations of SAEs based on their clinical judgment of likely causative factors. This may include clinical laboratory tests not specified in the protocol, histopathologic examinations, or consultations with specialists. The Sponsor or their designee may also request the investigator to conduct supplemental assessments.

If the SAE was not previously documented in the Investigator’s Brochure and is thought to be related to IP, the Sponsor or their designee may urgently require further information from the investigator for regulatory authority reporting. The Sponsor may need to issue an investigator Notification to inform all investigators involved in any clinical trial with the same drug that this SAE has been reported.

The investigator should notify Pharmacovigilance of any death or SAE occurring after a subject has withdrawn from the clinical trial when such a death occurs within 30 days of the last dose of IP and may reasonably be related to the IP.

### **8.6.3. Follow-up of Adverse Events**

All AEs will be followed until stabilization/resolution or until clinical database lock. AE’s are to be reported to the IRB in accordance with IRB policy.

All SAEs will undergo active follow-up until resolved or the event becomes chronic or stable. Follow-up data for SAEs obtained after clinical database lock will be incorporated into the safety database.

#### **8.6.4. Reporting Serious Adverse Events to Regulatory Health Authorities/ Institutional Review Boards/Research Ethics Boards/Independent Ethics Committees**

The investigator is responsible for following all local regulations for the reporting of safety information, including the reporting of SAEs to their local IRB/REB/IEC.

The investigator must promptly report to his or her local IRB/REB/IEC all unanticipated problems involving risks to subjects. This includes death from any cause and all serious adverse events reasonably or possibly associated with the use of IP.

The Sponsor or their designee is responsible for appropriate reporting of relevant AEs, suspected unexpected serious adverse reactions (SUSARs) involving IP, to all regulatory authorities.

In addition, the Sponsor or designee will be responsible for the submission of safety letters (e.g., SUSARs) to the central IRB/REB/IEC and to participating investigators of all SUSARs involving IP according to applicable regulations.

After termination of the clinical trial (determined as last subject, last visit), any unexpected safety issue that changes the risk-benefit analysis and is likely to have an impact on the subjects who have participated in it, will be reported by the Sponsor as soon as possible to the competent authority (ies) concerned together with proposed actions.

#### **8.7. Reporting Pregnancies**

Pregnancies for women will be reported from the time the subject signs the informed consent form through final clinical trial visit or 30 days after the last IP administration, whichever is later. Males will report pregnancy of their partners through 90 days after the last IP administration.

To ensure subject safety, each pregnancy in a subject on IP must be reported to Pharmacovigilance within 24 hours of learning of its occurrence. Subjects who become pregnant will be withdrawn from the clinical trial. The pregnancy should be followed up to determine outcome, including spontaneous or voluntary termination, details of the birth, and the presence or absence of any birth defects, congenital abnormalities, or maternal and/or newborn complications.

Pregnancy should be recorded on a subject's source documents and a Pregnancy Notification and Outcome Form and reported by the investigator to Pharmacovigilance using the same procedure for reporting SAEs detailed in Section 8.6.2. A pregnancy, by itself, is not an SAE. Pregnancy follow-up should also be recorded and should include an assessment of the possible relationship to the IP of any pregnancy outcome. Any pregnancy-related SAE (e.g., spontaneous abortion, birth defect) or any other SAE experienced during pregnancy must be recorded on a separate SAE Report Form and reported per SAE reporting procedures in Section 8.6.2.

## **9. STATISTICS HYPOTHESES AND METHODS OF ANALYSES**

### **9.1. Clinical Trial Populations**

#### **9.1.1. Intent-to-Treat (ITT)**

The Intent-to-Treat (ITT) population consists of all subjects who were randomized. All data will be included, and no subjects will be excluded because of protocol violations. All data will be included, and no subjects will be excluded because of protocol violations; subjects who have retinal detachment within 1-week post-operatively who will be deemed to have failed Day 0 (surgery) and will be removed from the efficacy analysis as per protocol per Section 2.2.1.

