**Primary Endpoint:**

The primary endpoint in Part 1 and Part 2 is the rate of recurrent retinal detachment requiring reoperation within 24 weeks from time of enrollment in drug-treated subjects compared to historical rates of retinal detachment for Grade C PVR. An evaluating investigator should determine whether the primary endpoint has been met. The primary endpoint requires verification by the Central Reading Center (CRC) before recurrent retinal detachment reoperation. In cases where CRC verification is not possible due to technical limitations with the Optical Coherence Tomography or fundus photograph, then the evaluating investigator will contact the trial medical monitor to confirm whether the primary endpoint has been met.

Recurrent retinal detachment is defined as either one, or, both of the following:

1. Spectral-Domain Optical Coherence Tomography (SD-OCT) demonstrating fovea-off retinal detachment (subfoveal fluid that is contiguous with a peripheral detachment);
2. Color fundus photographic documentation of a rhegmatogenous or tractional (or undetermined) retinal detachment that has progressed posterior to the Mandatory Reoperation Zone, as defined by a circle centered on the fovea, with a radius halfway between the arcades and the equator (Figure 2).

Stable, peripheral rhegmatogenous or tractional (or undetermined) detachments anterior to the mid-periphery may be observed or demarcated with laser at the Investigator's discretion and will not be counted as a failure.

Subjects who have retinal detachment within 1-week post-operatively will be deemed to have failed Day 0 (day of surgery) and will be removed from the efficacy analysis. Retinal detachment is defined as subjects who meet either of the recurrent retinal detachment imaging criteria as defined in the Primary Endpoint.

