In Part 1b of the GUARD study with activation of Protocol Version 5.0 (dated May 5 2021), eligible subjects will no longer be randomized and all enrolled subjects will be placed in the Intervention Cohort.

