#### **4.4. Handling of Subject Withdrawals or Subject Discontinuation of Clinical Trial Intervention**

Subjects that are dropped from the clinical trial prior to administration of the interventional investigational product or whom fail to achieve intraoperative complete retinal reattachment will be considered screen failures and will not be enrolled or included in analysis.

Subjects who have retinal detachment within 1-week post-operatively will be deemed to have failed Day 0 (day of surgery) and will be removed from the efficacy analysis. These will be considered “dropped” subjects.

Any subject receiving the investigational product will be followed for safety throughout the scheduled course of the clinical trial, or until the subject has reached a status of un-reachable.

It is anticipated that there will be a potential drop-out rate of up to 20%. To assure the clinical trial meets the required approximate 100 evaluable eyes for analysis, additional subjects may need to be enrolled to meet this goal.

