#### **9.1.2. Per-Protocol Population**

The Per-Protocol (PP) population is a subset of the ITT population and includes the subjects who completed the trial with no major protocol violations.

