## **9.3. Sample Size**

### **9.3.1. Sample Size Part 1**

The initial design of the GUARD Study was based on an recurrent retinal detachment rates of 0.2 and 0.5 for ADX-2191 and standard-of-care group, respectively. With a sample size of 90 subjects (45 per group) and 2-sided significant level at 0.05, the clinical trial would have approximately 80% power to detect the superiority of ADX-2191 over the standard-of-care.

The protocol was updated to an open-label, single arm study in Version 5.0.

Approximately 100 evaluable eyes will be recruited to complete the 24-week treatment period.

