#### **9.4.5. Primary Efficacy Analyses**

The primary efficacy variable of recurrent of retinal detachments (defined in Section 3.6) due to PVR requiring re-operation within six months from enrollment will be measured as binary variable (indicating recurrent of detachment or not). Briefly, a 95% confidence interval around the proportion of retinal detachment in drug-treated subjects will be generated, and the primary endpoint will have been deemed to have been met if the upper bound of the confidence interval is lower than the weighted average historical control detachment rate. The primary efficacy analyses will be conducted on the ITT population with observed data only. Subjects who discontinue investigational treatment early will be encouraged to stay for any remaining safety assessments until the conclusion of the clinical trial. Subjects who have retinal detachment within 1-week post-operatively will be deemed to have failed Day 0 (day of surgery), and will be removed from the efficacy analysis.

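### The ITT set is still limited to randomized subjects, so the single-arm primary test run on it leaves out every Part 1b subject

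*Combined protocol and SAP*

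**What the plan says.** - Section 9.1.1: "The Intent-to-Treat (ITT) population consists of all subjects who were randomized". The same section then removes subjects who detach within one week of surgery from the efficacy analysis.
- Section 9.1.2: "The Per-Protocol (PP) population is a subset of the ITT population".
- Section 9.4.5: "The primary efficacy analyses will be conducted on the ITT population with observed data only". Earlier in that paragraph, "a 95% confidence interval around the proportion of retinal detachment in drug-treated subjects will be generated", and the endpoint is met if the upper bound lies below the weighted historical rate.
- Section 3.2.2, on Part 1b: "eligible subjects will no longer be randomized and all enrolled subjects will be placed in the Intervention Cohort". The synopsis and Sections 3.1 and 6.10 say the same.
- Section 9.3.1: "The protocol was updated to an open-label, single arm study in Version 5.0".
- Synopsis, primary endpoint: the detachment rate "in drug-treated subjects compared to historical rates of retinal detachment for Grade C PVR".
- Section 4.4, on subjects who never receive product: "Subjects that are dropped from the clinical trial prior to administration of the interventional investigational product" are screen failures and are left out of the analysis.
- Section 9.4.6 specifies a logistic model for ADX-2191 against standard of care and an MMRM for BCVA. It names no analysis set for either.
- Sections 9.4.1 and 9.4.9 let a later SAP override the protocol, provided it is final before database lock. The public documents contain no SAP text on populations.

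**The concern.** A primary test needs one set of subjects, fixed in advance. Here the set definition and the success rule, which meet in the same section, point to different subjects. The ITT definition admits the Part 1a drug arm and the Part 1a controls and shuts out Part 1b. The success rule covers everyone given the drug. The two sets can give different verdicts on the same data. Because the trial is open-label, outcomes can be known before a SAP settles the choice. If the set is picked after that, the error rate is no longer that of one pre-specified test.

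There is a second consequence for the comparison with standard of care. Controls exist only in Part 1a. A set that pools Part 1b would compare non-randomized drug subjects, enrolled later, with those controls.

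**Working it through.** **The plan's own figure.** Section 9.3.1 gives about 80% power with 45 per group, rates 0.2 and 0.5, two-sided 0.05.
- Without continuity correction: n₀ = [1.96√(2·0.35·0.65) + 0.8416√(0.2·0.8 + 0.5·0.5)]² / 0.3² = 38.5, so 39 per group.
- With continuity correction: (38.5/4)·[1 + √(1 + 4/(38.5·0.3))]² = 44.9, so 45 per group.
- Power at 45 per group is 80.1% with continuity correction and 81.5% with Fisher's exact test.

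The figure reproduces, but it belongs to the superseded two-arm design. No power is stated for the single-arm test.

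**Who is in which set, read literally.**

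| Subjects | ITT (9.1.1) | Drug-treated (9.4.5, synopsis) |
|---|---|---|
| Part 1a, control | in | out |
| Part 1a, randomized to ADX-2191 and dosed | in | in |
| Part 1a, randomized to ADX-2191, never dosed | in (but out under 4.4) | out |
| Part 1b, dosed | out | in |

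The words drug-treated can filter controls out of ITT. They cannot bring non-randomized subjects into it. Only the safety set (9.1.3) is defined without reference to randomization, and it is assigned to safety analyses.

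**Size, as an illustration.** Assumptions, none of them given in the documents:
- The Part 1a/1b split. If R of 100 evaluable eyes were randomized 1:1, Part 1a has R/2 drug eyes and the whole trial has 100 − R/2. R = 40, 60 and 80 give 20 against 80, 30 against 70 and 40 against 60. If the 100 counts drug eyes only, which the 50 extra subjects in Section 3.1 would allow, 50 against 100 is possible.
- The historical rate p₀, taken as 0.35, 0.40, 0.45 and 0.50. The last is the standard-of-care rate in 9.3.1.
- The interval. Section 9.4.5 names no method, so I used Clopper-Pearson.

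Let c be the largest count whose upper 95% limit is below p₀. Power is P(X ≤ c) for X ~ Binomial(n, 0.20), with 0.20 from 9.3.1. At p₀ = 0.40, c is 3/20, 6/30, 9/40, 12/50, 16/60, 19/70, 23/80 and 30/100.

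Power, Part 1a drug eyes against all drug eyes:

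| p₀ | 20 vs 80 | 30 vs 70 | 40 vs 60 | 50 vs 100 |
|---|---|---|---|---|
| 0.35 | 21 vs 84% | 43 vs 78% | 44 vs 69% | 58 vs 91% |
| 0.40 | 41 vs 98% | 61 vs 95% | 73 vs 92% | 81 vs 99% |
| 0.45 | 63 vs >99% | 76 vs 99% | 91 vs 99% | 97 vs >99% |
| 0.50 | 80 vs >99% | 94 vs >99% | 98 vs >99% | 99 vs >99% |

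**Same observed rate, different verdict.** At 30% observed, the upper limit is 49.4% for 9/30 and 42.1% for 21/70. At a threshold of 0.45 the first fails and the second passes. At 0.40 both fail, and at 0.50 both pass.

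**Type I error if either set may be used.** Set the true rate equal to p₀ and nest the Part 1a eyes in the all-drug set. Then compute P(X ≤ c₁ or X + Y ≤ c₂), where X counts Part 1a events, Y counts Part 1b events, and c₁ and c₂ are the two limits. Over the first three pairs and four thresholds this is 2.3% to 3.7%, against 1.2% to 2.5% for a single fixed set. The nominal one-sided level is 2.5%.

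**The case against.** The strongest reply is that nobody would run the Part 1a-only test. The hypothesis in 9.2, the sample-size text in 9.3.1 and the success rule in 9.4.5 all describe a single-arm test against history, and restricting it to Part 1a would discard every subject enrolled under Version 5.0. On this view a leftover definition needs rewording, and the SAP can do that. This stands as a guide to intent, and it is why the power gaps are illustrations and not forecasts. It does not remove the contradiction: no section widens ITT. A SAP that need only be final before database lock is weak protection in an open-label trial.

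Three further points stand in part.
- The undosed-subject conflict is narrow. It concerns only Part 1a subjects randomized to ADX-2191 and never dosed, who should be few because the first injection is due on Day 0 or Day 1.
- The 63-point gap is one corner of the table. At 0.50 the gaps for the first three pairs are about 20, 6 and 2 points.
- The type I inflation is at most about 1.2 points above the nominal 2.5%. In two of the twelve scenarios the rate stays below nominal (2.33% and 2.46%). It also presumes selection after outcomes are seen, which nothing in the documents says will happen.

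Lastly, 9.4.6 adjusts for stratification factors, which belong to Part 1a randomization. That hints at the randomized set for the detachment model without naming it.

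**Conclusion.** The point holds. As written, the set for the only confirmatory test excludes all Part 1b subjects, and so does the per-protocol set. This contradicts the success rule, the synopsis endpoint and the single-arm description. It follows from the text alone and needs no assumption.

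The size does rest on assumptions about the split, the historical rate and the interval method. Under those used here, the power difference between the two sets runs from 63 points to under 1, and the sets can disagree at the same observed rate. Free choice between them would give a one-sided type I error of 2.3% to 3.7%. The intended set is not in serious doubt, but the sole primary test should not depend on inference.

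**What to change.** Amend Sections 9.1 and 9.4.5–9.4.6, and repeat the wording in the SAP, before open-label outcomes are reviewed:

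1. Define the primary efficacy set as all Intervention-cohort subjects: Part 1a randomized to ADX-2191 plus all of Part 1b. State whether at least one injection is required, so that 9.1, 4.4 and the success rule agree. Carry over the plan's one-week rule as it stands. Define per-protocol as a subset of this set.
2. Keep the all-randomized definition as the Part 1a ITT set and name it for the standard-of-care logistic model. I would use it for the BCVA MMRM too, and label any between-group comparison that pools Part 1b as descriptive. The contradiction itself does not force this last choice, but the plan should state one.
3. State which set applies in Part 2, since the primary endpoint covers both parts.

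The cost is a few lines of text, with no new data and no new patients.

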#### **9.1.2. Per-Protocol Population**

The Per-Protocol (PP) population is a subset of the ITT population and includes the subjects who completed the trial with no major protocol violations.

#### **9.1.3. Safety Population**

The safety population includes all subjects who received the test article. The safety population will be analyzed as treated and will be used for the safety analyses. No data will be excluded for any reason.

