Overall Design: In Part 1a of the GUARD Study (prior to activation of Protocol Version 5.0, dated May 5 2021), eligible subjects will be randomized 1:1 intraoperatively to either the Control or Intervention cohort. Subjects in the Control cohort will receive Standard Procedures only. In Part 1b of the GUARD Study (after activation of Protocol Version 5.0, dated May 5 2021), eligible subjects will no longer be randomized and all enrolled subjects will be placed in the Intervention Cohort. Subjects in the Intervention cohort will receive Standard Procedures and intravitreal ADX-2191 injections (Figure 1). In Part 1a, stratification will be used to balance treatment assignments within key subgroups. Subjects are to be stratified by clinical presentation (recurrent retinal detachment vs. OGI) and number of recurrent retinal detachments (>3 vs. ≤3). Subjects enrolled in Part 1 will not be eligible to participate in Part 2 nor will they be eligible to be randomized again during Part 1. Clinical trial procedures to be conducted in Part 1 and Part 2 are outlined in the Schedule of Assessments (Table 1).		

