## **9.4. Statistical Analysis**

### **9.4.1. General Considerations**

Prior to database lock, the Sponsor will finalize a statistical analysis plan (SAP) detailing all planned analyses. Any analyses conducted in addition to those specified in the SAP will be clearly documented as post hoc. A summary of the currently planned analyses for the primary and secondary outcome variables is found below.

Quantitative variables will be summarized descriptively using number of subjects (n), mean, standard deviation, median, minimum, and maximum. Qualitative variables will be summarized using counts and percentages.

All summaries will be presented by treatment group. Summaries will be provided for demographics, baseline medical history, concurrent therapies, and subject disposition.

For the purpose of summarization, medical history, concurrent therapies, and adverse events will be coded to MedDRA and WHO Drug dictionaries, as appropriate.

All analyses will be two-sided at a significance level of 0.05. The 95% confidence intervals will be provided where appropriate.

The primary endpoint analysis will compare retinal detachment rates of drug-treated subjects to a historical control rate, which will be a weighted average of the retinal re-detachment rates from two prior Grade C PVR prospective clinical trials with similar inclusion criteria (Banerjee, 2017; Schiff, 2007).

The SAP will serve as the final determinant of the statistical procedures, notwithstanding language herein.

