#### **9.4.7. Safety Analysis**

Safety endpoints analyzed in Part 1 and Part 2 include:

- BCVA at distance utilizing an ETDRS chart
- IOP
- Slit-lamp evaluation
- Dilated ophthalmoscopy
- Adverse event (AE) query (reported, elicited, and observed)

Adverse events will be coded using the MedDRA dictionary. Frequencies and percentages will be provided per treatment group of subjects with treatment-emergent adverse events (TEAEs), serious TEAEs, and TEAEs causing premature discontinuation. An adverse event is treatment-emergent if it occurs or worsens after the first dose of investigational treatment. Furthermore, frequencies will be given of subjects with TEAEs by system organ class, by system organ class and preferred term, by system organ class, preferred term and maximal severity, by system organ class, preferred term and strongest relationship, and by system organ class, preferred term, maximal severity, and strongest relationship.

All evaluations of safety will be described in the SAP.

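### As written, Part 1a Control cannot appear in the promised by-group safety tables, and the AE/SAE end date differs between sections, with three of them giving Control none

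*Combined protocol and SAP*

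**What the plan says.** **Who is analyzed for safety.** Section 9.1.3: "The safety population includes all subjects who received the test article". The same section makes this set the basis of the safety analyses, as treated. The Synopsis lists ADX-2191 as the only test product and says of Part 1a: "Subjects in the Control cohort will receive Standard Procedures only".

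**What counts as treatment-emergent.** Section 8.5: "A TEAE is defined as an AE that occurred during the clinical trial after the first dose of IP". Section 9.4.7: "An adverse event is treatment-emergent if it occurs or worsens after the first dose of investigational treatment". Section 8.1 describes an AE as something that happens to a patient who was given an investigational product (IP).

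**What is promised.** Section 9.4.1: "All summaries will be presented by treatment group". Section 9.4.7: "Frequencies and percentages will be provided per treatment group of subjects with treatment-emergent adverse events (TEAEs"), together with serious TEAEs and TEAEs that lead to discontinuation.

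**Where the detail is to go.** Section 9.4.7: "All evaluations of safety will be described in the SAP". Section 9.4.1, repeated in 9.4.9: "The SAP will serve as the final determinant of the statistical procedures, notwithstanding language herein".

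**When collection ends.** Sections 6.6 and 8 (opening) for AEs, and 8.6.2 for SAEs, stop 30 days after the last IP administration. Section 8.3 records AEs up to the final trial visit. Section 7.16 collects AEs at Week 24, but refers back to 6.6 and 8 and sets no end date itself. Section 8.7 uses the later of the two dates, for pregnancies in women only.

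**The concern.** Safety is part of the primary objective (Synopsis, 2.1.1), and Part 1a is the one stage for which the protocol describes randomization against a concurrent Control. If the stated definitions are followed, TEAE rates on ADX-2191 will stand with no concurrent rate beside them. Events of surgery, silicone oil and the underlying disease could then not be set against what happened in eyes without injections. Control remains in use for efficacy: section 9.4.6 fits a logistic regression of ADX-2191 against standard-of-care.

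The second issue is separate and concerns instructions to sites. An SAE that starts more than 30 days after the last injection but before Week 24 falls inside 8.3 and outside the timeframe in 8.6.2. For a Control subject, the three IP-anchored sections give no stop date at all. Precedence of the SAP over statistical procedures does not settle this, because these are reporting rules for investigators.

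**Working it through.** The plan gives no figure on this point, so there is nothing to reproduce. Part 1 compares definitions; part 2 is day arithmetic.

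**Part 1: can Control appear in the tables?**

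1. The safety set requires receipt of the test article (9.1.3), and the only test product is ADX-2191 (Synopsis). Control has none (Synopsis, 3.1). Control subjects in the set: 0, apart from any who were injected in error.
2. A TEAE requires a first dose (8.5, 9.4.7). Control has no first dose. Control TEAEs: 0. This would hold even if 9.1.3 were widened, so changing 9.1.3 alone is not enough.
3. Read literally, 8.1 does not cover events in a subject who was never given IP.
4. The tables are nevertheless to be shown by treatment group (9.4.1, 9.4.7). The definitions and the tables cannot both stand for Part 1a.
5. The data are scheduled. The note to Table 1 has Control attend Visits 1, 2, 3, 4, 7, 11, 13, 15 and 16. Sections 7.2, 7.3, 7.4, 7.7, 7.11, 7.13, 7.15 and 7.16 list AE collection at each of these after screening: 8 visits.
6. Intervention also has AE collection at Visits 5, 6, 8, 9, 10, 12 and 14: 7 more, so 8 + 7 = 15 against 8.

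**Part 2: how far apart are the end dates?**

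Inputs: last scheduled injection at Week 16 (6.11); the 30-day rule (6.6, 8, 8.6.2); final visit at Week 24, with a window of 2 weeks either way (section 7). Days are counted from surgery, with Week w taken as day 7w.

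- Full course: 7 × 16 = 112, and 112 + 30 = day 142. Final visit: 7 × 24 = day 168. Gap: 168 − 142 = **26 days**.
- If the window applies in both directions, the visit falls on days 154 to 182 and the gap is 12 to 40 days. This is an assumption, because section 7 also asks for at least 24 weeks.
- Last injection at Week w, with follow-up to Week 24: gap = 168 − (7w + 30) = 138 − 7w. For w = 8: 138 − 56 = **82 days**. For w = 4: 138 − 28 = **110 days**. The case arises under 6.9, where a recurrence needing a return to the operating room ends injections but not follow-up.
- The order can reverse. Section 3.7 brings the end-of-study visit forward when treatment stops early. Assume a last injection at Week 8 (day 56) and that visit at Week 10 (day 70). The 30-day rule then ends on day 86, which is 86 − 70 = 16 days after the visit. Neither rule is always the longer.
- Control: there is no last injection, so the 30-day rule cannot be evaluated. Only 8.3 gives an end date.

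The TEAE definitions have a start but no cut-off, so an event recorded late under 8.3 in a dosed subject would still be a TEAE. The window conflict therefore bears on what sites collect and report, and not on how TEAE is defined.

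**The case against.** **The trial is now single-arm.** Since Version 5.0 (9.3.1) the primary comparison is with a historical rate, so a treated-only safety set may be what the sponsor wants. That is plausible, and BCVA, a listed safety endpoint, is still modelled with a treatment term in 9.4.6. But the current text keeps Control, compares it for efficacy and promises by-group safety tables. If the restriction is intended, it has to be stated.

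**The SAP will deal with it.** It may. A reader might infer that Control has been finally excluded from safety reporting. The documents do not support that: the SAP governs, and it is to be completed before database lock. Nor do they support the opposite inference, because no SAP text supplied redefines the safety set or the start of treatment emergence.

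**The window conflict is editorial.** Much of this stands. A reader might infer that SAEs will be lost. The documents do not show that: 8.3 still records the event, 8.4 asks whether it is serious, 8.6.2 opens by requiring every SAE whatever its cause, and 3.3 has safety monitored to the last scheduled assessment. What remains is two stop dates for sites and none for Control in three sections.

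**A side-by-side table would mislead.** This stands as a caution. Intervention is asked about AEs at seven more visits and the trial is open-label, so more AEs may be found on ADX-2191 for that reason alone. Starting the count at surgery would also include events that precede a first injection given on Day 1 (6.11). Both points limit what the table can show and belong in its design. They are not a reason to leave Control unreported.

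**Conclusion.** Both parts hold as defects of the text and should be corrected.

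1. Under 9.1.3, 8.5 and 9.4.7, with 8.1, Part 1a Control is absent from the by-group safety tables. The number of subjects affected cannot be given, because the documents do not say how many were randomized in Part 1a. It would be too firm to say that the effect is confined to Part 1a. Section 3.1 restricts Control to that part, yet the Synopsis and 9.3.2 still size Part 2 at 50 to 150 per treatment.
2. The AE/SAE end dates differ by a nominal 26 days after a full course, and by 82 or 110 days when injections stop at Week 8 or Week 4 and follow-up continues to Week 24. These figures assume visits on their nominal days. The finding is an inconsistent reporting window; loss of SAE data is not shown.

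Including Control would not make the Part 1a comparison free of ascertainment bias.

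**What to change.** **Part 1, in the protocol or the governing SAP.**

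- Define the Safety population as all subjects who received ADX-2191 plus Part 1a subjects assigned to Control who had Day 0 surgery, analyzed as treated. State how Intervention subjects who were never injected are handled, consistently with 4.4.
- Extend 8.1 to Control.
- Keep the first-dose TEAE definition for the ADX-2191 tables.
- For the Part 1a side-by-side table, start both arms at Day 0 surgery and flag events that precede a Day 1 first injection.
- Report AEs found at the shared visits (2, 3, 4, 7, 11, 13, 15 and 16) separately or as a sensitivity table.
- If ADX-2191-only tables are intended after Version 5.0, say so in 9.4.1 and 9.4.7, and state where Control AEs are reported.
- Reconcile the per-treatment sizing of Part 2 (Synopsis, 9.3.2) with Control being limited to Part 1a (3.1).

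This costs definitions and one or two more tables. It needs no new visits, since Control AEs are already scheduled.

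**Part 2, in the protocol.** Reconcile 6.6, 8, 8.3 and 8.6.2 to one AE/SAE window that also covers Control. One option is the later-of-two-dates rule already used in 8.7, with the final visit as the end for Control. The cost is text in four sections and a longer SAE reporting period: nominally 26 days more for fully dosed subjects, and longer for those who stop injections early but stay in follow-up.
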